8.3.2 Technical Computational Details for Exploratory Endpoint Analyses

To do the by visit analysis of exploratory endpoints #1 and #2, CDAI remission and PRO-2 remission will be determined at Weeks 2, 4, 6, 8, and 10, in addition to Week 12, using the same definition in session 8.1.1 and session 8.2.1. At each visit, subjects' status of dosage increase of baseline Crohn's disease medications, taking a new medication for Crohn's disease during the double blind treatment period and withdraw from the trial during the double blind period will be checked. If any of these scenarios is observed, the subject will be considered as treatment failure – non remission.

8.4 Handle of Multiplicity for Efficacy Analyses

To control the family-wise error rate (FWE) of multiple comparisons at alpha level of 0.05, the average effect method as a global test ² and the hierarchical testing procedure as a gatekeeping strategy will be applied to the primary and secondary endpoints.

In order to handle multiplicity issue in the analysis of the primary efficacy endpoint, the average treatment difference of the pooled OPS-2071 600 mg BID and 300 mg BID treatment groups with placebo will be tested first at 2-sided alpha level of 0.05. If this global test is significant, then comparisons for each dose group of OPS 2071 600 mg BID and 300 mg BID versus placebo will be performed at 2-sided alpha level of 0.05. The comparison of a dose group is significant at 0.05 FWE significant level if both the global test and the test of the dose group's comparison with placebo are significant at alpha level of 0.05. If both null hypotheses of OPS-2071 600 mg BID, and 300 mg BID in the primary endpoint are rejected with an experiment wise Type I error of 0.05, a formal test of the secondary efficacy endpoint of endoscopic response for comparisons of OPS-2071 600 mg BID versus placebo and 300 mg BID versus placebo will be conducted, using a similar procedure used for the primary endpoint. If both null hypotheses of OPS-2071 600 mg BID versus placebo and 300 mg BID versus placebo in this secondary efficacy endpoint are rejected with an experiment wise Type I error of 0.05, the formal comparison of OPS-2071 150 mg BID versus placebo in the primary efficacy endpoint will be conducted, using the same model provided in section 8.1.2 for the primary analysis. If the null hypothesis of the primary efficacy endpoint of OPS-2071 150 mg BID is rejected with experiment wise Type I error of 0.05, the formal comparison of OPS-2071 150 mg BID versus placebo in the secondary efficacy endpoint of endoscopic response will be conducted, using the same model provided in the section 8.2.1 for the analysis of this secondary efficacy endpoint. Formal analyses of other secondary efficacy endpoints will start if the null hypothesis of OPS-2071 150 mg BID in the secondary efficacy endpoint of endoscopic response is rejected with experiment wise Type I error of 0.05.

The other secondary efficacy endpoints of this trial will be tested by the order of the gatekeeping test procedure. Formal test of the secondary efficacy endpoint #2 will start with a comparison of pooled OPS-2071 600 mg BID and 300 mg BID versus placebo. If it is significant, comparisons of 600 mg BID versus placebo and 300 mg BID versus placebo will be performed. If both these two comparisons are significant, formal comparison of OPS-2071 150 mg BID versus placebo will be conducted for the secondary efficacy endpoint #2. If this comparison is again significant, analysis of the secondary efficacy endpoint #3 will start using the same procedure, up to the secondary

efficacy endpoint #6.: Overall, this analytical procedure along with the gatekeeping protects the experiment wise Type I error in the primary and secondary analyses.

9 Safety Analyses

9.1 Extent of Exposure

Extent of exposure to the trial medication for safety sample will be summarized using descriptive statistics (n, percentage).

9.2 Adverse Events

All AEs will be coded by system organ class and the Medical Dictionary for Regulatory Activities preferred term. The incidence of the following events will be summarized by treatment group:

- TEAEs
- TEAEs by severity
- TEAEs potentially causally related to the IMP
- TEAEs with an outcome of death
- Serious TEAEs
- TEAEs leading to discontinuation of the IMP

The TEAEs from the start of IMP to the first day of bowel preparation for ileocolonoscopy will be included in the TEAE summaries for all subjects who have bowel preparation for ileocolonoscopy at Week 12. The TEAEs that occur during the ileocolonoscopy preparation and procedure will be summarized separately.

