3.5.2.2 Secondary Safety Endpoint

The secondary safety endpoint is the percentage of subjects by specific AEs, which will be recorded with the onset date, resolution or stabilization date, severity grade, and relatedness to IMP.

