^oDetermine the SES-CD after the Week 12 ileocolonoscopy has been completed.

^pCollect a fecal sample for the FCP and microbiota assessment approximately 5 days prior to the Week 12 (eg, Day 79) visit date, prior to the bowel preparation and ileocolonoscopy; this is to ensure that subjects are taking IMP when these assessments are completed.

^qCollect a fecal sample for the microbiota assessment prior to the bowel preparation and ileocolonoscopy.

^rThe 3-day bowel preparation (consisting of 2 days of dietary modifications and 1 day of cleansing bowel preparation) should be approximately 4 days prior to the Week 12 (eg, Day 80 through Day 82) visit date; this is to ensure that subjects are taking IMP when this assessment is completed. An ileocolonoscopy with biopsy will be conducted up to approximately 1 day prior to the Week 12 (eg, Day 83) visit date. The ileocolonoscopy will be centrally read. The bowel preparation and ileocolonoscopy with biopsy will not be performed at the End of Treatment visit.

^sAt Week 12, only the morning dose of IMP will be administered.

^tThe blood samples for the FBR and CRP assessments will be collected prior to the first dose on Day 1.

^uIf CRP is not elevated on Day 1, there is no need for any further CRP assessments.

^vA daily diary will be completed by subjects throughout the trial (see [Section 3.7.2.4](#)).

Protocol 341-201-00004

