3.7.1.9 Week 12 (+ 2 days)/End of Treatment

The following assessments will occur at Week 12 (around Day 84)/End of Treatment:

- Subjects will complete a daily diary (see [Section 3.7.2.4](#))
- Record the date and time of dose administration in eSource
- Take vital signs (blood pressure, heart rate, body temperature, and respiratory rate)
- Perform a urine pregnancy test for WOCBP (if the urine pregnancy test result is positive, the investigator must follow-up with a confirmatory serum pregnancy test)
- Perform a 12-lead standard safety ECG
- Collect blood samples for PK analysis 1 to 4 hours after the morning dose at the same time as the collection of blood samples for clinical laboratory tests
- Collect blood samples for hematology and serum chemistry, and a urine sample for urinalysis
- Collect a blood sample for the CRP assessment (not needed if CRP is not elevated on Day 1)
- Perform a physical examination (including body weight)
- Determine the CDAI score (for the Week 12 visit, follow the specific assessment as outlined below)
- Collect a fecal sample for the FCP and microbiota assessment (for the Week 12 visit, follow the specific assessment as outlined below)
- All unused IMP will be collected, and final IMP accountability will be performed
- Review and record any concomitant medications
- Assess and record any AEs

The subject must be taking IMP when the following assessments are completed. In order to ensure this occurs, the following schedule must be followed for Week 12 only:

- Collect a fecal sample for the FCP and microbiota assessment approximately 5 days prior to the Week 12 (eg, Day 79) visit date, prior to the bowel preparation and ileocolonoscopy
- Assess the first 3 elements of the CDAI prior to the bowel preparation:
 - Number of liquid or soft stools each day for 7 days
 - Abdominal pain (graded from 0 - 3 on severity) each day for 7 days
 - General well-being, subjectively assessed from 0 (well) to 4 (terrible) each day for 7 days
- The 3-day bowel preparation (consisting of 2 days of dietary modifications and 1 day of cleansing bowel preparation) should be approximately 4 days prior to the Week 12 (eg, Day 80 through Day 82) visit date

Protocol 341-201-00004

- An ileocolonoscopy with biopsy will be conducted up to approximately 1 day prior to the Week 12 (eg, Day 83) visit date. The ileocolonoscopy will be centrally read.
- Determine the SES-CD after the Week 12 ileocolonoscopy has been completed

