3.7.3.4 Electrocardiogram Assessments

The 12-lead ECGs will be performed in the supine position.

At the sparse blood sampling sites, standard safety ECGs will be conducted during the screening period; predose on Day 1; 1 to 4 hours postdose on Day 1, Day 8, Week 2, Week 6, and Week 12/End of Treatment; and at the 30-day post-treatment follow-up.

At the robust blood sampling sites, triplicate ECGs will be recorded on Day 1 and Week 6 at predose (prior to the morning dose) and at 2, 4, and 8 hours after the morning dose. The 3 ECG replicates will be extracted from a 5-minute “ECG window” (typically, the last 5 minutes of the 15-minute period when the subject is maintained in a supine position). There will be at least 1 minute between each ECG. Baseline will be the average of the 3 ECG measurements conducted in triplicate at predose on Day 1. Blood samples for PK analysis should be taken immediately following the triplicate ECG assessments. Additional standard safety ECGs will be conducted during the screening period; 1 to

Protocol 341-201-00004

4 hours postdose on Day 8, Week 2, and Week 12/End of Treatment; and at the 30-day post-treatment follow-up visit.

Subjects should be monitored for potentially clinically significant ECG results. Any abnormalities considered by the investigator to be clinically significant are to be recorded as AEs on the AE screen in eSource.

The ECGs should be performed before blood sample collection, when applicable. A central ECG service will be utilized for reading all ECGs. Additional ECGs may be conducted based on local regulatory requirements, as needed.

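### SAP 9.2 ends the main TEAE summaries at the first day of Week 12 bowel preparation and gives TEAEs starting from the Week 12 visit onward no stated place

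*SAP*

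**What the plan says.** SAP 9.2 lists six TEAE incidence summaries by treatment group and then sets a window for them: "The TEAEs from the start of IMP to the first day of bowel preparation for ileocolonoscopy will be included in the TEAE summaries". The window applies "for all subjects who have bowel preparation for ileocolonoscopy at Week 12". The next sentence adds: "The TEAEs that occur during the ileocolonoscopy preparation and procedure will be summarized separately". Protocol 7.6.1 has the same two sentences, so it does not settle anything the SAP leaves open. Neither section says where a TEAE that starts after the ileocolonoscopy is counted.

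The protocol puts the procedure before the final treatment visit: "An ileocolonoscopy with biopsy will be conducted up to approximately 1 day prior to the Week 12 (eg, Day 83) visit date". At the Week 12 visit itself the site must still "Assess and record any AEs", and Protocol 3.7.1.10 repeats that instruction for the 30-day follow-up. A Table 3.7-1 footnote says the morning dose of IMP is given at Week 12. Another limits the preparation to subjects who reach Week 12: "The bowel preparation and ileocolonoscopy with biopsy will not be performed at the End of Treatment visit".

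**The concern.** Setting aside events confounded by bowel preparation is sensible. The text does this by ending the main window when preparation begins, and it never reopens the window once the procedure is over. On that reading the main incidence tables lose onsets on the last dosing day and any later treatment-emergent onsets as well as the preparation events.

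This matters for three reasons.

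- **Endpoint.** Protocol 3.5.2.2 states: "The secondary safety endpoint is the percentage of subjects by specific AEs". The affected tables are the main display by arm for that endpoint.
- **Unequal windows.** The cut-off applies only to subjects who have the preparation. A subject who leaves at an early End of Treatment visit has none. If discontinuation differs by arm, so does the period over which AEs are counted; the direction cannot be known in advance.
- **A scheduled safety visit falls in the gap.** Week 12 has a postdose ECG, hematology, chemistry, urinalysis and a physical examination. Protocol 3.7.3.4 says of ECGs: "Any abnormalities considered by the investigator to be clinically significant are to be recorded as AEs on the AE screen in eSource".

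**Working it through.** The plan gives no figure to reproduce, so the check is a day count on the protocol's example days.

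**Inputs**

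- Bowel preparation: Days 80 to 82 (Table 3.7-1 footnotes; Protocol 3.7.1.9).
- Ileocolonoscopy: Day 83 (same places).
- Week 12 visit and last dose for an on-treatment completer: about Day 84, window + 2 days (Protocol 3.7.1.9).
- Follow-up: 30 days after treatment, ± 2 days (Protocol 3.7.1.10).
- End of the treatment-emergent period: not shown in the text available for review. Three ends are assumed: last dose, last dose + 7 days, last dose + 30 days.

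**Where each day falls**

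- Main TEAE summaries: Day 1 to Day 80.
- Separate summary: Day 80 to Day 83, which is 83 − 80 + 1 = 4 days. Day 80 can fall in both windows.
- Neither: Day 84 onward.

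**Size of the gap**

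Gap days = (assumed end day) − (Week 12 visit day) + 1. Share = gap days ÷ assumed end day.

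| Assumed end | Visit on Day 84 | Visit on Day 86 |
|---|---|---|
| Last dose | 1/84 = 1.2% | 1/86 = 1.2% |
| Last dose + 7 days | 8/91 = 8.8% | 8/93 = 8.6% |
| Last dose + 30 days | 31/114 = 27.2% | 31/116 = 26.7% |

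With the Week 12 visit on Day 84, counting to a follow-up visit 2 days early or late instead gives 29/112 = 25.9% to 33/116 = 28.4%.

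**Scheduled assessments in the gap, even with the shortest end**

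- Postdose ECG visits on treatment: Day 1, Day 8, Week 2, Week 6, Week 12. One of five is in the gap (20%).
- Serum chemistry visits on treatment after the first dose: Day 8, Week 2, Week 6, Week 12 (Weeks 4, 8 and 10 are hematology only). One of four is in the gap (25%).

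**Possible cover elsewhere**

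SAP Appendix 4 lists no table titled for post-procedure or follow-up TEAEs. Table CT-8.1, adverse events of all causalities, states no window and might count later onsets. Deaths, SAEs and trial discontinuations due to AEs have listings CT-9.1 to CT-9.3, which preserve the events but do not give incidence by arm. The ECG and laboratory tables under SAP 9.3 and 9.6 have no such cut-off.

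**The case against.** The best defence is that SAP 9.2 says earlier TEAEs are included and does not say that only those are. The list of summaries above the sentence has no date limit. The stated end point could merely mark where the main tables hand over to the preparation summary, with the text silent on what follows. It is true that there is no explicit exclusion. But silence still leaves post-procedure onsets unassigned, and if they were meant to be in the main tables, the end point would need a matching restart. Two programmers could build different tables from these sentences.

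The size is also open to challenge. The end of the treatment-emergent period is not visible in the text reviewed, so the 9% and 27% figures are scenarios. The example days are approximate, and a procedure closer to the visit would shrink the on-treatment gap below one day. Both points stand.

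The shares of visits can look larger than they are. A symptom reported at Week 12 may have begun at any time since Week 10, so mainly findings first detected by that day's tests would have a Week 12 onset. Other denominators give lower shares: Week 12 is 1 of 8 on-treatment visits with AE assessment (12.5%) and 1 of 7 hematology visits after the first dose (14%). This limits what the 20% and 25% figures show. They are shares of visits and not estimates of lost events.

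Finally, deaths, SAEs and trial discontinuations due to AEs stay in listings, and no bias between arms has been shown. The likely loss is therefore mainly non-serious late events that did not lead to discontinuation.

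**Conclusion.** The concern holds on the natural reading of SAP 9.2 and Protocol 7.6.1. For subjects with the Week 12 preparation, TEAEs starting from the Week 12 visit onward have no place in either stated summary, while subjects who leave at an early End of Treatment visit are not cut off. An event after the Day 84 dose would be treatment-emergent on any usual definition, so the existence of the gap does not depend on the unseen end date; only its length does. That length is 1% of observation days at the shortest assumed end and about 27% at the longest. How many events this represents cannot be derived from the documents.

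Confidence is moderate, because the exclusion is inferred from a stated end point and not written as a rule. SAP section 11 records early termination with three randomized subjects and says the planned analyses will not be performed. The point therefore corrects the plan as written and changes no reported result.

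**What to change.** Reword SAP 9.2 and Protocol 7.6.1 so that the carve-out depends on onset during preparation and procedure, and everything else stays in the main tables. For example:

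> For subjects with bowel preparation at Week 12, TEAEs with onset during the preparation or ileocolonoscopy are summarised separately. All other TEAEs, including those with onset after the ileocolonoscopy through the end of the TEAE period applied to every subject, are included in the main TEAE incidence tables.

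The sentence should point to the place where the end of the TEAE period is defined, or state that end if no definition exists, so that the handling of follow-up events is clear. Classifying by onset also removes the overlap on the first preparation day.

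The cost is wording in two sections and minor programming. No new data are needed. Displayed AE counts would be slightly higher, by an amount that depends on how many TEAEs start after the procedure.

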9.3 Clinical Laboratory Data

Summary statistics for changes from baseline in the central clinical laboratory measurements will be provided for the safety sample. Potentially clinically significant results in laboratory tests identified using prospectively defined criteria, including criteria for liver enzyme elevations, will also be summarized for the safety sample. By-subject listings will be provided for data of local laboratory tests.

In addition, According to FDA Guidance,³, laboratory measurements that signal the potential for Hy's Law will be reported. An incidence table and a listing will be provided for subjects who meet one or combinations of the following criteria, without initial findings of cholestasis (alkaline phosphatase activity > 2 times the ULN):

- ALT or AST \geq 3 times the ULN
- Bilirubin \geq 2 times the ULN

9.4 Vital Sign Data

Summary statistics for changes from baseline in vital signs and potentially clinically significant results in vital signs will be summarized for the safety sample.

9.5 Physical Examination Data

By-subject listings will be provided for physical examinations.

9.6 Electrocardiogram Data

The mean change from baseline and the incidence of clinically significant changes will be calculated for ECG parameters.

For the analysis of QT and the corrected QT interval (QTc), data from 3 consecutive complexes (representing 3 consecutive heart beats) will be measured to determine average values. The following QT corrections will be used for reporting purposes in the clinical study report:

1) QTcF is the length of the QT interval corrected for heart rate by the Fridericia formula: $QTcF = QT / (RR)^{0.33}$

QTcN is the length of the QT interval corrected for heart rate by the FDA Neuropharm Division formula: $QTcN = QT / (RR)^{0.37}$

A regression analysis will be used to derive the slope and its 90% confidence interval of the change in QTc, adjusted from the placebo effect ($\Delta\Delta QTc$), against the drug concentration by robust blood sampling visit.

10 Interim Analysis

No interim analysis is planned for this trial.

11 Changes in the Planned Analyses

The planned analyses will not be performed due to the early termination of the trial with only three randomized subjects.

12 References

- 1 Yuan Y. Sensitivity analysis in multiple imputation for missing data. Proceedings of the SAS Global Forum Conference; 2014 Mar 23-26; Washington, DC; 2014.
- 2 Guidance for Industry, Drug-Induced Liver Injury: Premarketing Clinical Evaluation. US Department of Health and Human Services, Food and Drug Administration, and Center for Drug Evaluation and Research (CDER), July 2009.

13 Appendices

Appendix 1 Criteria for Identifying Vital Signs and Weight of Potential Clinical Relevance

Variable	Criterion Value ^a	Change Relative to Baseline ^a
Heart Rate ^b	> 120 bpm < 50 bpm	≥ 15 bpm increase ≥ 15 bpm decrease
Systolic Blood Pressure ^b	> 180 mmHg < 90 mmHg	≥ 20 mmHg increase ≥ 20 mmHg decrease
Diastolic Blood Pressure ^b	> 105 mmHg < 50 mmHg	≥ 15 mmHg increase ≥ 15 mmHg decrease
Orthostatic Hypotension	≥ 20 mmHg decrease in systolic blood pressure and a ≥ 25 bpm increase in heart rate from supine to sitting/standing	Not Applicable
Weight	-	≥ 7% increase ≥ 7% decrease

^aIn order to be identified as potentially clinically relevant, an on-treatment value must meet the “Criterion Value” and also represent a change from the subject’s baseline value of at least the magnitude shown in the “Change Relative to Baseline” column.

^bAs defined in “Supplementary Suggestions for Preparing an Integrated Summary of Safety Information in an Original NDA Submission and for Organizing Information in Periodic Safety Updates,” FDA Division of Neuropharmacological Drug Products draft (2/27/87).

Appendix 2 Criteria for Identifying Laboratory Values of Potential Clinical Relevance

Laboratory Tests	Criteria
Chemistry^a	
AST (SGOT)	≥ 3 x upper limit of normal (ULN)
ALT (SGPT)	≥ 3 x ULN
Alkaline phosphatase	≥ 3 x ULN
LDH	≥ 3 x ULN
BUN	≥ 30 mg/dL
Creatinine	≥ 2.0 mg/dL
Uric Acid	
Men	≥ 10.5 mg/dL
Women	≥ 8.5 mg/dL
Bilirubin (total)	≥ 2.0 mg/dL
CPK	≥ 3 x ULN
Prolactin	> ULN
Hematology^a	
Hematocrit	
Men	≤ 37 % and decrease of ≥ 3 percentage points from Baseline
Women	≤ 32 % and decrease of ≥ 3 percentage points from Baseline
Hemoglobin	
Men	≤ 11.5 g/dL
Women	≤ 9.5 g/dL
White blood count	≤ 2,800/ mm ³ or ≥ 16,000/ mm ³
Eosinophils	≥ 10%
Neutrophils	≤ 15%
Absolute neutrophil count	≤ 1,000/ mm ³
Platelet count	≤ 75,000/ mm ³ or ≥ 700,000/ mm ³
Urinalysis^a	
Protein	Increase of ≥ 2 units
Glucose	Increase of ≥ 2 units
Casts	Increase of ≥ 2 units
Additional Criteria	
Chloride	≤ 90 mEq/L or ≥ 118 mEq/L
Potassium	≤ 2.5 mEq/L or ≥ 6.5 mEq/L
Sodium	≤ 126 mEq/L or ≥ 156 mEq/L
Calcium	≤ 8.2 mg/dL or ≥ 12 mg/dL
Glucose	
Fasting	≥ 115 mg/dL
Non-Fasting	≥ 200 mg/dL
Total Cholesterol, Fasting	≥ 240 mg/dL
LDL Cholesterol, Fasting	≥ 160 mg/dL
HDL Cholesterol, Fasting	≤ 30 mg/dL
Triglycerides, Fasting	
Men	≥ 160 mg/dL
Women	≥ 120 mg/dL

^aAs defined in “Supplementary Suggestions for Preparing an Integrated Summary of Safety Information in an Original NDA Submission and for Organizing Information in Periodic Safety Updates,” FDA Division of Neuropharmacological Drug Products draft (2/27/87).

Appendix 3 Criteria for Identifying ECG Measurements of Potential Clinical Relevance

Variable	Criterion Value ^a	Change Relative to Baseline ^a
Rate		
Tachycardia	≥ 120 bpm	increase of ≥ 15 bpm
Bradycardia	≤ 50 bpm	decrease of ≥ 15 bpm
Rhythm		
Sinus tachycardia ^b	≥ 120 bpm	increase of ≥ 15 bpm
Sinus bradycardia ^c	≤ 50 bpm	decrease of ≥ 15 bpm
Supraventricular premature beat	all	not present → present
Ventricular premature beat	all	not present → present
Supraventricular tachycardia	all	not present → present
Ventricular tachycardia	all	not present → present
Atrial fibrillation	all	not present → present
Atrial flutter	all	not present → present
Conduction		
1° atrioventricular block	PR ≥ 0.20 second	increase of ≥ 0.05 second
2° atrioventricular block	all	not present → present
3° atrioventricular block	all	not present → present
Left bundle-branch block	all	not present → present
Right bundle-branch block	all	not present → present
Pre-excitation syndrome	all	not present → present
Other intraventricular conduction block ^d	QRS ≥ 0.12 second	increase of ≥ 0.02 second
Infarction		
Acute or subacute	all	not present → present
Old	all	not present → present ≥ 12 weeks post trial entry
ST/T Morphological		
Myocardial Ischemia	all	not present → present
Symmetrical T-wave inversion	all	not present → present
Increase in QTc	QTc > 450 msec (males and females)	

^aIn order to be identified as potentially clinically relevant, an on-treatment value must meet the “Criterion Value” and also represent a change from the subject’s baseline value of at least the magnitude shown in the “Change Relative to Baseline” column.

^bNo current diagnosis of supraventricular tachycardia, ventricular tachycardia, atrial fibrillation, atrial flutter, or other rhythm abnormality.

^cNo current diagnosis of atrial fibrillation, atrial flutter, or other rhythm abnormality.

^dNo current diagnosis of left bundle branch block or right bundle branch block.

